3 LIST OF ABBREVIATIONS AND DEFINITIONS OF TERMS

Abbreviation	Term
AE	adverse event
ALT	alanine aminotransferase
ANC	absolute neutrophil count
AST	aspartate aminotransferase
ATC Level 1	anatomical therapeutic chemical class
ATC Level 3	Pharmacological class
AUC _(0-t)	area under the concentration-time curve from zero time (pre-dose) to the time of last quantifiable concentration
AUC _(0-inf)	area under the concentration-time curve from zero time (pre-dose) extrapolated to infinite time
β -hCG	beta-human chorionic gonadotropin
BLQ	Below the limit of quantification
BMI	body mass index
BOR	best overall response
BSA	body surface area
BUN	blood urea nitrogen
CBR	clinical benefit rate
CI	confidence interval
CL	total clearance
C _{max}	maximum observed concentration
CR	complete response
CRF	Case Report Forms
CTCAE	Common Terminology Criteria for Adverse Events
CV	coefficient of variation
C1D1	Cycle 1 Day 1

Abbreviation	Term
DCR	disease control rate
DLT	dose-limiting toxicity
DOE	duration of response
EAS	Evaluable Analysis Set
ECG	Electrocardiogram
ECI	Events of Clinical Interest
ECOG	Eastern Cooperative Oncology Group
ER	estrogen
FDA	US food and drug administration
FAS	Full Analysis Set
HER-2	human epidermal growth factor receptor 2
irAE	immune-related adverse events
irRECIST	Immune-related Response Evaluation Criteria In Solid Tumors
IV	Intravenous
LDH	Lactate Dehydrogenase
LLT	lower level term
LLOQ	lower limit of quantification
MedDRA	Medical Dictionary for Regulatory Activities
MRI	magnetic resonance imaging
MRT	mean residence time
mTNBC	metastatic triple-negative breast cancer
NCA	Non-compartmental analysis
NCI	National Cancer Institute
NE	not evaluable
ORR	objective response rate

Abbreviation	Term
OS	overall survival
PK/PD	Pharmacokinetic/pharmacodynamics
PD	progressive disease
PD-L1	programmed death-ligand 1
PFS	progression-free survival
PP	predictive probability
PR	Partial Response
PT	preferred term
Q1	first quantile
Q3	third quantile
RBC	red blood cell
RDI	relative dose intensity
RECIST 1.1	Response Evaluation Criteria in Solid Tumors (version 1.1)
RP2D	recommended Phase 2 dose
SAE	serious adverse event
SAP	Statistical Analysis Plan
SD	stable disease
SD	standard deviation
SMQ	Standardized MedDRA Queries
SOC	system organ class
$t_{1/2}$	terminal elimination phase half-life
T4	thyroxine
TEAE	treatment-emergent adverse event
t_{\max}	time at which the highest drug concentration occurs
t_{last}	the time of the last measurable (positive) concentration.

Abbreviation	Term
TSH	thyroid stimulating hormone,
TTR	time to response
ULN	upper limit normal
UNK	unknown response
Vz	volume of distribution at terminal phase
WBC	white blood cells
WHO DD	WHO Drug Dictionary

4 INTRODUCTION

The purpose of this statistical analysis plan (SAP) is to describe the procedures and the statistical methods that will be used to analyze the efficacy and safety variables and report results for Eisai Protocol E7389-M001-218, An Open-Label Single-Arm Multicenter Phase 1b/2 Study to Evaluate the Efficacy and Safety of Eribulin Mesylate in Combination with Pembrolizumab in Subjects with Metastatic Triple Negative Breast Cancer (mTNBC). The focus of this SAP is for the planned primary, secondary and exploratory efficacy and safety analyses during the interim monitoring and at the final analysis in the study. The analysis details for Pharmacokinetic, Pharmacodynamics, Pharmacogenomics, and Biomarker analyses are not described herein this SAP. Separate analysis plans will be completed for these specific analysis variables and attached to the final SAP and clinical study report.

Reference materials for this statistical analysis plan (SAP) include the protocol amendment 04 of E7389-M001-218 (dated 2019-05-29) and Case Report Forms (CRF, Version, 2017-2-21). If the protocol or case report forms are amended or updated then appropriate adjustments to the SAP may be made if they are related to the planned analyses.

The SAP described hereafter is an *a priori* plan. This is an open label study and the SAP will be finalized and approved before database lock. Statistical programming may occur as study data accumulate in order to have analysis programs ready at the time the study finishes.

4.1 Study Objectives

In subjects with mTNBC previously treated with 0 (Stratum1) or 1 to 2 (Stratum 2) lines of systemic anticancer therapy in the metastatic setting and currently treated with eribulin mesylate in combination with pembrolizumab:

4.1.1 Primary Objective

- For the Phase 1b part – to determine safety and tolerability of eribulin mesylate in combination with pembrolizumab in all subjects (ie, Stratum 1 and 2).
- For the Phase 2 part – to evaluate objective response rate (ORR) per Response Evaluation Criteria in Solid Tumors version 1.1 (RECIST 1.1) by independent imaging review (IIR) in all subjects.
- For the Phase 2 part – to evaluate ORR per RECIST 1.1 by IIR in Stratum 2 subjects and compare with the historical response rate of pembrolizumab monotherapy of 10%.

4.1.2 Secondary Objectives

- For the Phase 2 part, in all subjects and separately in Stratum 2 subjects, to evaluate Progression-Free Survival (PFS) per RECIST 1.1 by IIR.
- To evaluate Overall Survival (OS).
- To evaluate Duration of Response (DOR) per RECIST 1.1 by IIR.
- To evaluate Clinical Benefit Rate (CBR) per RECIST 1.1 by IIR.

- To evaluate efficacy outcomes (ORR, PFS, DOR and CBR) per RECIST 1.1 by investigator review.
- To evaluate efficacy outcomes (ORR, PFS, DOR and CBR) per RECIST 1.1 by IIR and OS outcome by PD-L1 (programmed death receptor-ligand 1) expression.
- To evaluate the safety and tolerability of the combination.

4.1.3 Exploratory Objectives

- To evaluate time to response (TTR) per RECIST 1.1 by IIR in all subjects and separately in Stratum 2 subjects.
- To evaluate exposure-response relationship in all subjects.
- To explore potential effects of pembrolizumab co-administration on the pharmacokinetics (PK) of eribulin mesylate in all subjects.
- To explore efficacy outcomes (ORR, PFS, DOR, and CBR) per immune-related RECIST 1.1 (irRECIST) by IIR and investigator review for all subjects and separately in Stratum 2 subjects.

4.2 Overall Study Design and Plan

This is an open-label, single-arm, multicenter, Phase 1b/2 study of eribulin mesylate in combination with pembrolizumab in subjects with metastatic triple-negative breast cancer previously treated with 0 to 2 lines of systemic anticancer therapy (cytotoxic or targeted anticancer agents) in the metastatic setting. Subjects may have received prior neo/adjuvant chemotherapy.

The Phase 1b part includes 1 initial safety run-in cohort in which at least 6 subjects will receive eribulin mesylate 1.4 mg/m² intravenously (IV) on Days 1 and 8 of a 21-day cycle and pembrolizumab 200 mg IV on Day 1 of a 21-day cycle (dose level 1). Dose-limiting toxicity (DLT) will be assessed in the first cycle. Dose level 1 can be selected as the recommended Phase 2 dose (RP2D) if no more than 1 subject has a DLT. Otherwise, eribulin mesylate dose will be lowered from 1.4 mg/m² to 1.1 mg/m² on Days 1 and 8 of a 21-day cycle (dose level 0). If no more than 1 out of 6 subjects at dose level 0 has a DLT, the Phase 2 part will proceed with dose level 0. Approximately 12 subjects may be enrolled in the Phase 1b part of the study.

Under protocol amendment 1, 107 subjects (including subjects in Phase 1b who are on RP2D level) were enrolled in 2 strata and received the same combination treatment at the RP2D level. The strata include no prior systemic anticancer therapy in the metastatic setting (Stratum 1) and previously treated with 1 to 2 lines of systemic anticancer therapy in the metastatic setting (Stratum 2). Bayesian predictive probability (PP) of response rate was used to monitor the response rate after postbaseline tumor assessments for at least 38 subjects were available. The study could be stopped early for efficacy or futility if PP crosses the prespecified boundary. Hence, efficacy conclusion of the primary efficacy endpoint of ORR could be made on the basis of the predictive probability prior to the full enrollment of 100 evaluable subjects in the study .

There is clinical interest to have a more precise estimation of the efficacy data for Stratum 2. Therefore, per protocol amendment 3, additional subjects will be added to Stratum 2 in order to include a total of 80 evaluable subjects in Stratum 2 for final analysis. As a result, approximately 150 subjects in total (145 evaluable with 80 in Stratum 2) will be enrolled. Per protocol amendment 4, additional subjects will be added to Stratum 2 in order to include a total of at least 100 evaluable subjects in Stratum 2 for final analysis.

5 DETERMINATION OF SAMPLE SIZE

A total of approximately 170 subjects (165 evaluable with 80 in Stratum 2) will be enrolled.

Under protocol amendment 1, 107 subjects including at least 6 from the Phase 1b part were enrolled in the study. Enrollment was into 2 strata, which included first-line (Stratum 1) versus second- and third-line (Stratum 2) subjects. Bayesian predictive probability was used to monitor the study after response data from the first 38 subjects were available. Sample size calculation was carried out assuming the historical response rate of 0.2. Using simulation, the model parameters ($\theta_L=0.025$, $\theta_U=0.99$, and $\theta_T=0.95$) were calibrated such that the frequentist 1-sided Type I error was 0.0326 when the tumor response rate in the combination regimen was 0.2 (under frequentist's null hypothesis H_0), and the power was 0.9278 when the response rate was 0.35 (under frequentist's alternative hypothesis H_a). The expected numbers of subjects needed to reach the decisions were 56 and 61 when $p=0.2$ (under H_0) and 0.35 (under H_a), respectively. A vague beta prior distribution for response rate, p , was specified in PP calculation; that is, $p\sim\text{beta}(0.2, 0.8)$. PP was updated for every 3 new subjects in the simulations, which mimics the group sequential decision making in a real trial setting. Without Bayesian interim monitoring, the Type I error was estimated as 0.0358, and power was estimated as 0.9418 in demonstrating posterior probability $P(p>0.2|\text{data})\geq0.95$. Five thousand simulations were run to estimate these design characteristics.

Per protocol amendment 3, additional subjects will be enrolled to ensure 80 evaluable subjects in Stratum 2. Using binomial exact test, the power is 0.92 with 80 evaluable subjects to demonstrate statistical significance at 1-sided alpha of 0.025 for the assumptions of H_0 : ORR=0.10 vs. H_a : ORR=0.25. With 80 subjects, the 95% confidence interval for ORR from binomial distribution will be 0.160-0.359 if the observed ORR is 0.25.

Per protocol amendment 4, additional subjects will be added to Stratum 2 in order to include a total of at least 100 evaluable subjects in Stratum 2 for final analysis.

6 STATISTICAL METHODS

All descriptive statistics for continuous variables will be reported using mean, standard deviation (SD), median, Q1, Q3, minimum and maximum. Categorical variables will be summarized as number (percentage) of subjects.

6.1 Study Endpoints

RECIST 1.1 criteria will be used in the evaluation of tumor status for the primary, secondary and exploratory endpoints, irRECIST criteria will be used in the evaluation of tumor status for one of the exploratory endpoints. Tumor response data obtained per RECIST 1.1 by IIR will be utilized in the main analysis of ORR, PFS and DOR. In addition, tumor assessment data assessed per RECIST1.1 by investigator review and per irRECIST by IIR and by investigator review will be considered as secondary or exploratory (CTCAE, 2009).

6.1.1 Primary Endpoint

Objective Response Rate (ORR) - defined as the proportion of subjects who had best overall response (BOR) of Complete Response (CR) or Partial Response (PR).

6.1.2 Secondary Endpoints

The secondary efficacy endpoints are as follows:

- **Progression-Free Survival (PFS)** - defined as the time from date of first dose of study drug to date of first documentation of disease progression or death, whichever occurs first.
- **Overall Survival (OS)** – defined as the time from the date of first dose of study drug until date of death from any cause.
- **Duration of Response (DOR)** – defined as the time from the date that a confirmed objective response is first documented to the date of PD or death due to any cause for those subjects with a confirmed PR or CR.
- **Clinical Benefit Rate (CBR)** – defined as the proportion of subjects who had BOR of CR, PR, or durable SD (≥ 24 weeks).
- Estimates of ORR, PFS, OS and DOR in the PD-L1 Positive Set.

6.1.3 Exploratory Endpoints

- **Time to Response (TTR)** – defined as the time from the first dose date to the date that the confirmed objective response is first documented for subjects who had BOR of CR or PR based on RECIST 1.1.
- **ORR, BOR, PFS, DOR, CBR and DCR** using irRECIST

6.2 Study Subjects

6.2.1 Definitions of Analysis Sets

The DLT Evaluable Set includes subjects in Phase 1b who complete the first treatment cycle (i.e., take at least 2 doses of eribulin mesylate with no more than one dose reduction and at least 1 dose of

pembrolizumab). Subjects in phase 2 who had a DLT event will be considered evaluable for the dose-limiting toxicity as well. It is the analysis set for DLT evaluation in the Phase 1b part.

The Full Analysis Set (FAS) (Safety Analysis Set) includes all subjects who received any amount of either study drug. This is the analysis set for safety analyses and analyses of PFS and OS.

The Evaluable Analysis Set (EAS) (subset of Full Analysis Set) includes all subjects treated at RP2D level who have both an evaluable baseline tumor assessment and an evaluable postbaseline tumor assessment, unless discontinued early or death. It is the analysis set for efficacy analyses.

The PD-L1 Positive Set (subset of Evaluable Analysis Set) includes evaluable subjects whose PD-L1 expression level is above the threshold that is to be specified prior to the final analysis. Key primary and secondary efficacy endpoints (i.e., ORR, PFS, OS, and DOR) will be summarized in this analysis set.

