9.4.5 Selection and Timing of Dose for Each Subject

All subjects will receive pembrolizumab first, followed immediately by eribulin mesylate on Day 1 of each cycle. On Day 8 of each cycle, the subjects will receive eribulin mesylate only.

The Phase 1b part includes 1 initial safety run-in cohort in which 6 subjects will receive eribulin mesylate 1.4 mg/m² intravenously (IV) on Days 1 and 8 of a 21-day cycle and pembrolizumab 200 mg IV on Day 1 of a 21-day cycle (Dose Level 1). Dose-limiting toxicity will be assessed in the first cycle as described in [Section 9.1](#).

In the Phase 2 part subjects will receive the RP2D of eribulin mesylate IV on Days 1 and 8 of a 21-day cycle and pembrolizumab 200 mg IV on Day 1 of a 21-day cycle.

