9.5.1.3 Treatment/End of Treatment Assessments

Treatment and End of Treatment assessments are listed in the Schedule of Procedures/Assessments ([Table 8](#)).

Dose-limiting toxicity (DLT) assessments will be conducted for Phase 1b subjects. A DLT is defined as one of the following toxicities occurring during the DLT assessment window and considered by the investigator to be related to either of the study drugs.

Hematologic Toxicities:

- Any Grade 4 thrombocytopenia or neutropenia lasting >7 days

Nonhematologic Toxicities:

- Episcleritis, uveitis, or iritis of Grade 2 or higher
- Any Grade 4 toxicity
- Any Grade 3 toxicity EXCLUDING:
 - Nausea/vomiting/diarrhea controlled by medical intervention within 72 hours
 - Grade 3 rash in the absence of desquamation, no mucosal involvement, does not require steroids, and resolves to Grade 1 by the next scheduled dose of pembrolizumab
 - Transient Grade 3 AST or ALT elevation, defined as no more than 3 days with or without steroid use
- Discontinuation or delay of more than 2 weeks of either study medication due to treatment-related AE will be considered as a DLT

All subjects enrolled in Phase 1b will be assessed for DLTs during a DLT assessment window of the first cycle of 21 days. Subjects who discontinue study treatment prior to completing the DLT assessment window for any reason other than a DLT will be replaced.

End of Treatment assessments for all subjects will be collected within 30 days of the last dose of study drug. Subjects with SAEs and/or ECIs at the time of End of Treatment will be followed for 90 days after the last dose of study drug or, if the subject initiates new anticancer therapy, for 30 days following the last dose of study drug, whichever is earlier.

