9.7.1.2 Definitions of Analysis Sets

- The DLT Evaluable Set includes subjects who complete the first treatment cycle (ie, take at least 2 doses of eribulin mesylate with no more than 1 dose reduction and at least 1 dose of pembrolizumab) and have sufficient safety evaluation. Subjects who had a DLT event will be considered evaluable for the dose-limiting toxicity as well. It is the analysis set for DLT evaluation in the Phase 1b part.
- The Full Analysis Set (Safety Analysis Set) includes all subjects who received any amount of either study drug. This is the analysis set for safety analyses and analysis of PFS and OS.
- The Evaluable Analysis Set (subset of Full Analysis Set) includes all subjects who have both an evaluable baseline tumor assessment and an evaluable postbaseline tumor assessment, unless discontinued early or death. It is the analysis set for efficacy analyses.

- The PD-L1 Positive Set (subset of Evaluable Analysis Set) includes evaluable subjects whose PD-L1 expression level is above the threshold that is to be specified prior to the final analysis. Key primary and secondary efficacy endpoints (ie, ORR, PFS, OS, and DOR) will be summarized in this analysis set.

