9.7.1.8 Safety Analyses

Safety analyses will be performed for the Safety Analysis Set. Safety data that will be evaluated include AEs, clinical laboratory results, vital signs, and ECGs. Safety will be summarized separately for subjects enrolled in Phase 1b and Phase 2 and combined, unless otherwise specified in the SAP.

RP2D and DLT

The Phase 1b study will include at least 1 safety run-in cohort in which 6 metastatic triple-negative breast cancer (mTNBC) subjects who receive eribulin mesylate 1.4 mg/m² on Days 1 and 8 and pembrolizumab 200 mg on Day 1 of a 21-day cycle (Dose Level 1). Subjects will be observed for dose-limiting toxicity (DLT) in the first cycle. The purpose of the safety run-in cohort(s) is to study safety of the 2-drug combination. The Phase 2 part will proceed with Dose Level 1 when no more than 1 subject has a DLT. Otherwise, a lower eribulin mesylate dose of 1.1 mg/m² and pembrolizumab 200 mg will be evaluated in another cohort of 6 subjects. If no more than 1 subject has a DLT in the first cycle, the Phase 2 part will proceed with Dose Level 0 as the RP2D. Otherwise, alternative doses (eribulin mesylate 0.7 mg/m²) will be explored prior to the start of the Phase 2 part.

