9.7.1.8.2 ADVERSE EVENTS

Dose-limiting toxicity in the first cycle will be used to determine the RP2D. The DLT rate will be summarized descriptively at each combination dose level in the DLT evaluable set. Subsequent dose-limiting toxicity will be reported and summarized as well.

The AE verbatim descriptions (investigator terms from the CRF) will be classified into standardized medical terminology using Medical Dictionary for Regulatory Activities (MedDRA). Adverse events will be coded to the MedDRA (Version 17 or higher) lower level term (LLT) closest to the verbatim term. The linked MedDRA preferred term (PT) and primary system organ class (SOC) are also captured in the database.

A TEAE is defined as an AE that had an onset date, or a worsening in severity from baseline (pretreatment), on or after the first dose of study drug administration up to 30 days (90 days for SAEs and/or ECIs) following study drug discontinuation.

Only those AEs that were treatment emergent will be included in summary tables. All AEs, treatment-emergent or otherwise, will be presented in subject data listings.

The incidence of TEAEs will be reported as the number (percentage) of subjects with TEAEs by SOC and PT. A subject will be counted only once within an SOC and PT, even if the subject experienced more than 1 TEAE within a specific SOC and PT. The number (percentage) of subjects with TEAEs will also be summarized by CTCAE v4.03.

The number (percentage) of subjects with TEAEs will also be summarized by relationship to each study drug. Treatment-related TEAEs include those events considered by the investigator to be possibly or probably related to study treatment or with missing assessment of the causal relationship. Serious adverse events (SAEs), deaths, TEAE with Grade 3 or above, and TEAEs that led to treatment discontinuation, dose reduction or dose interruption will be summarized.

Adverse events of clinical interest, described in [Section 9.5.4.3.2](#), will be summarized descriptively. Details will be provided in the SAP.

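### SAP 6.2.1 drops the protocol's safety-evaluation condition from the DLT Evaluable Set, so a Phase 1b subject lost to observation after the Day 8 dose counts as DLT-free

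*SAP*

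**What the plan says.** **Protocol.** Section 9.7.1.2 and the matching synopsis entry define the DLT Evaluable Set by a dosing minimum (two eribulin doses with at most one reduction, one pembrolizumab dose) plus a second condition: "at least 1 dose of pembrolizumab) and have sufficient safety evaluation". Any subject with a DLT is evaluable as well.

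**SAP.** Section 6.2.1 has Phase 1b subjects who "complete the first treatment cycle (i.e., take at least 2 doses of eribulin mesylate with no more than one dose reduction" and who had at least one pembrolizumab dose. The definition stops there. The next sentence extends evaluability to subjects with a DLT, but only to those in Phase 2.

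**Window and replacement.** Protocol 9.5.1.3 states: "All subjects enrolled in Phase 1b will be assessed for DLTs during a DLT assessment window of the first cycle of 21 days". It continues: "Subjects who discontinue study treatment prior to completing the DLT assessment window for any reason other than a DLT will be replaced".

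**Use of the set.** Protocol 9.7.1.8.2 states: "The DLT rate will be summarized descriptively at each combination dose level in the DLT evaluable set".

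**Deviations.** Protocol 9.7.5 requires the SAP to document any departure from the protocol's analysis plan. The SAP documents none on this point.

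**The concern.** A DLT rate is interpretable only if the subjects counted as free of DLT were watched long enough for one to appear. The protocol's second condition provides for this. Without it, the SAP admits a subject on dose counts alone, and those counts can be met well before the window closes. Some DLT criteria need time to resolve: Grade 4 neutropenia or thrombocytopenia must last more than 7 days, so an episode starting on Day 9 cannot qualify before about Day 16 (9 + 7).

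A subject who drops out of sight after the Day 8 dose for a non-DLT reason adds one to the denominator and nothing to the numerator. The error can therefore only lower the reported rate or leave it unchanged. The set supplies the denominator of a Phase 1b safety summary in a cohort of 6 to about 12 subjects, where one misclassified subject is visible.

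**Working it through.** The documents give no operating characteristic for the DLT rule, so there is no planned figure to reproduce. The check compares the texts and adds simple arithmetic.

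**1. The two definitions.**

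| Element | Protocol 9.7.1.2 and synopsis | SAP 6.2.1 |
|---|---|---|
| At least 2 eribulin doses, at most 1 reduction | yes | yes |
| At least 1 pembrolizumab dose | yes | yes |
| Safety-evaluation condition | yes | absent |
| Subjects with a DLT are evaluable | all | Phase 2 only |

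**2. When the SAP minimum is met.** Both drugs are given on Day 1. Protocol 9.4.5 adds: "On Day 8 of each cycle, the subjects will receive eribulin mesylate only". The second eribulin dose is thus due on Day 8, and no later Cycle 1 dose is planned. Days left in the window: 21 − 8 = 13, and 13/21 = 62%.

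**3. Who falls in the gap.**
- Stopping because of a treatment-related event is already counted: "Discontinuation or delay of more than 2 weeks of either study medication due to treatment-related AE will be considered as a DLT". Only exits for other reasons matter.
- Protocol 9.5.5 says that stopping treatment is not withdrawal from the study, and 9.5.1.6.1 collects adverse events for 30 days after the last dose. After a Day 8 dose, collection runs to about Day 38 (8 + 30), beyond Day 21. A subject who only stops treatment is normally still observed through the window.
- That leaves subjects who withdraw consent or are lost between Day 8 and Day 21. Those who start other anticancer treatment in that interval are partly affected, because 9.5.1.6.1 then ends reporting of non-serious events.

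**4. Effect on the rate (illustration).** Take 6 fully observed subjects with 1 DLT, and let k replaced subjects stay in the set with their replacements. Rate = 1/(6 + k):
- k = 0: 1/6 = 16.7%
- k = 1: 1/7 = 14.3%, which is 2.4 points lower
- k = 2: 1/8 = 12.5%

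With no DLT the rate is 0 whatever the denominator.

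**5. The neighbouring clause.** Suppose the one DLT among 6 Phase 1b subjects occurs before the second eribulin dose. Under the protocol the rate is 1/6 = 16.7%. Read literally, the SAP excludes that subject, because the dosing minimum is not met and the DLT clause covers Phase 2 only. The rate becomes 0/5 = 0%.

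**The case against.** **The SAP still requires completion of the cycle, and SAP 6.6.2 defines a cycle as 21 days.** That reading is available, but 6.2.1 itself explains completion by listing doses, and 6.6.2 credits an eribulin cycle after a single dose on Day 1 or Day 8. The 21-day definition does not repair the set.

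**The protocol never defines its own condition, so restoring the words would not by itself exclude an early leaver.** This stands. The protocol describes cycle completion by the same dose counts. The link to Day 21 has to be written in; it cannot simply be copied back.

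**The SAP nowhere says that a replaced subject stays in the denominator.** True, but nothing in 6.2.1 removes such a subject, and neither document says how replaced subjects are counted.

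**Two stronger readings a reader might infer.**
- That every subject who stops after Day 8 is observed for less than half the window. The documents do not support this, since adverse event collection continues after treatment stops.
- That dose selection was compromised. The rule is a count of DLTs: "The Phase 2 part will proceed with Dose Level 1 when no more than 1 subject has a DLT". Section 9.1 of the protocol records the recommended Phase 2 dose as already determined, and nothing in the documents shows that this set's definition influenced the choice.

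**The effect is hypothetical and touches only a descriptive rate.** This also stands: no document reports such a subject, and no test or remaining decision uses the rate. It limits the importance of the point but does not remove the conflict between the two texts.

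**Conclusion.** The point holds in a limited form. The SAP's stated definition conflicts with the protocol's without a recorded deviation, and the conflict can only lower the reported DLT rate or leave it unchanged. It affects Phase 1b subjects who received the Day 8 dose and then, for a non-DLT reason, were not observed for safety to the end of the window.

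Its size is about 2 percentage points per such subject in the illustration, which assumes six fully observed subjects, one DLT, and a replaced subject kept alongside the replacement. Whether any such subject exists cannot be told from the documents. The restriction of the DLT clause to Phase 2 can matter more, because taken literally it can remove a DLT from the numerator.

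**What to change.** Reconcile SAP 6.2.1 with protocol 9.7.1.2 in one edit:

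1. Keep the existing dosing and dose-reduction criteria and restore the safety-evaluation condition.
2. Make that condition checkable by tying it to safety observation through the 21-day DLT window. The protocol leaves the phrase undefined, so the SAP should state this as its operational definition.
3. State how subjects replaced under protocol 9.5.1.3 are handled in the denominator, including those who stopped treatment but were still observed through Day 21.
4. Remove the restriction to Phase 2 from the clause on subjects with a DLT, so that Phase 1b subjects with a DLT stay evaluable whatever their dose count or follow-up.

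If the sponsor prefers the dose-count definition, the SAP should record it as a deviation under protocol 9.7.5. The list of early Phase 1b exits should then be shown next to the DLT rate.

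The cost is a few sentences in the SAP and at most the reclassification of a few Phase 1b subjects. No new data are needed.

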9.4.1.1 Eribulin Mesylate Dose Modification During Treatment

Eribulin mesylate dose may need to be delayed and reduced during the study. Dose interruption and dose reduction instructions for subjects who experience eribulin mesylate toxicity are presented in [Table 3](#).

Recommended dose delays:

- Do not administer eribulin mesylate on Day 1 or Day 8 for any of the following:

- Absolute neutrophil count (ANC) <1,000/mm³
- Platelets <75,000/mm³
- Grade 3 or 4 nonhematological toxicities
- Eribulin mesylate Day 8 dose may be delayed for a maximum of 1 week.
 - If toxicities do not resolve or improve to ≤ Grade 2 severity by Day 15, omit the dose.
 - If toxicities resolve or improve to ≤ Grade 2 severity by Day 15, administer eribulin mesylate at a reduced dose and initiate the next cycle no sooner than 2 weeks later.

Recommended dose reductions:

If a dose has been delayed for toxicity and toxicities have recovered to Grade 2 severity or less, resume eribulin mesylate at a reduced dose as set out in Table 3.

Do not re-escalate the mesylate eribulin dose after it has been reduced.

Table 3 Eribulin Mesylate Dose Adjustments for Toxicity

Adverse Reaction / Toxicity ^a	Eribulin Mesylate Dose Modification
Permanently reduce the 1.4 mg/m ² eribulin mesylate dose for any of the following: ANC <500/mm ³ for >7 days ANC <1,000/mm ³ with fever or infection Platelets <25,000/mm ³ Platelets <50,000/mm ³ requiring transfusion Non-hematologic Grade 3 or 4 toxicities Omission or delay of Day 8 eribulin mesylate dose in previous cycle for toxicity	1.1 mg/m ²
Occurrence of any event requiring permanent dose reduction while receiving 1.1 mg/m²	0.7 mg/m ²
Occurrence of any event requiring permanent dose reduction while receiving 0.7 mg/m²	Discontinue eribulin mesylate
If unable to administer a scheduled dose of eribulin mesylate for more than 21 days of study, discuss with sponsor prior to continuing treatment	

ANC = absolute neutrophil count.

a: Toxicities graded in accordance with National Cancer Institute Common Terminology Criteria for Adverse Events, Version 4.03 (NCI-CTCAE, v 4.03).

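### SAP 6.2.1 rescues only Phase 2 subjects with a DLT, so, read literally, a Phase 1b subject whose DLT prevented the second eribulin dose leaves the set used for the Phase 1b DLT rate

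*SAP*

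**What the plan says.** **SAP 6.2.1** builds the DLT Evaluable Set in two steps. Phase 1b subjects enter if they completed the first cycle, which means they "take at least 2 doses of eribulin mesylate with no more than one dose reduction" and had at least one pembrolizumab dose. A second sentence then adds: "Subjects in phase 2 who had a DLT event will be considered evaluable for the dose-limiting toxicity as well". The definition ends: "It is the analysis set for DLT evaluation in the Phase 1b part".

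**Protocol 9.7.1.2**, and the synopsis in the same words, has the add-on without a phase limit: "Subjects who had a DLT event will be considered evaluable for the dose-limiting toxicity as well".

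**Protocol 9.5.1.3** says who is assessed: "All subjects enrolled in Phase 1b will be assessed for DLTs during a DLT assessment window of the first cycle of 21 days". It also says who is replaced: "Subjects who discontinue study treatment prior to completing the DLT assessment window for any reason other than a DLT will be replaced".

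**Protocol 9.7.1.8.2** reports the DLT rate at each dose level in the DLT evaluable set. SAP 6.6.1 repeats the dose-selection rule and names no other denominator. Protocol 9.7.5 requires departures from the protocol's analysis plan to be recorded in the SAP; SAP 6.2.1 records none.

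**The concern.** The add-on exists to keep subjects whose DLT stopped them from completing cycle 1. They have no other route into the set, and they carry the event being counted. The SAP gives this protection to Phase 2, where the protocol provides for no DLT assessment, and withholds it in Phase 1b, where the rate is wanted.

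At stake is the reported Phase 1b DLT rate. Safety and tolerability in Phase 1b is a primary objective in both documents, and the DLT rate is its planned summary by dose level. A programmer following the SAP text could report 0% when a DLT had occurred.

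**Working it through.** The documents state no DLT count or rate, so there is no figure to reproduce. The check has two parts: whether the excluded case can arise under the protocol's own rules, and how far it moves the rate.

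**1. Can a Phase 1b subject have a DLT and only one eribulin dose?**

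- Protocol 9.5.1.3: "Discontinuation or delay of more than 2 weeks of either study medication due to treatment-related AE will be considered as a DLT". A subject who stops eribulin for a treatment-related event after Day 1 and before Day 8 therefore has a DLT and exactly one dose. In this case the exclusion follows directly.
- Protocol 9.4.1.1 withholds the Day 8 dose for Grade 3 or 4 nonhematologic toxicity, which overlaps the DLT list in 9.5.1.3. It continues: "If toxicities do not resolve or improve to ≤ Grade 2 severity by Day 15, omit the dose". A subject with such a DLT can therefore also end cycle 1 with one dose.
- A DLT that occurs after the second dose does not by itself remove the subject.

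The replacement rule in 9.5.1.3 covers only those who stop for a reason other than a DLT. Subjects who stop because of a DLT are therefore meant to be counted.

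**2. Effect on the rate**

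Let *n* be the Phase 1b subjects at the dose level who are evaluable under the protocol, *d* those with a DLT, and *e* those with a DLT but no second eribulin dose.

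- Protocol rate: *d*/*n*
- Literal SAP rate: (*d* − *e*)/(*n* − *e*)
- Difference: *d*/*n* − (*d* − *e*)/(*n* − *e*) = *e*(*n* − *d*)/[*n*(*n* − *e*)], which is never negative. The exclusion cannot raise the rate.

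Inputs:

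- *n* = 6 to 12, the minimum and maximum for the Dose Level 1 cohort in Protocol 9.1.
- *d* ≤ 1, because Dose Level 1 became the recommended Phase 2 dose (Protocol 9.1) under a rule allowing at most one subject with a DLT (Protocol 9.1, SAP 6.6.1).
- *e* = 1 is an assumption, the only case with an effect at this dose level.

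| *n* | Protocol rate | Literal SAP rate | Difference |
|---|---|---|---|
| 6 | 1/6 = 16.7% | 0/5 = 0% | 16.7 percentage points |
| 12 | 1/12 = 8.3% | 0/11 = 0% | 8.3 percentage points |

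If *e* = 0, the two definitions give the same rate on this point.

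**3. The Phase 2 clause**

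If DLTs are recorded only in Phase 1b, as 9.5.1.3 implies, the clause adds nobody. If *k* Phase 2 events were recorded as DLTs, each would add one to numerator and denominator: (*d* − *e* + *k*)/(*n* − *e* + *k*). Those subjects would enter because of the outcome alone, and Phase 2 subjects without a DLT would not enter at all.

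**The case against.** The strongest reply is that this is a wording slip, not a chosen analysis. The SAP's own closing sentence makes a Phase 2 add-on visibly misworded. The SAP does not itself plan a DLT rate; that comes from the protocol, whose definition keeps every subject with a DLT. No document shows that any subject was affected, the dose is already selected, and the events still appear in the adverse event tables for the Safety Analysis Set.

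Most of this is true and limits the weight of the point. It does not remove it. The SAP is the document written to govern the analysis, and nothing else in it brings these subjects back. The adverse event tables are not a substitute, because SAP 6.6 presents safety by stratum and combined, so they would not show the Phase 1b DLT rate.

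Two further objections stand in part. First, the protocol's unrestricted sentence, read literally, would also admit a Phase 2 subject with a DLT, so that weakness is not the SAP's alone. Second, limiting the add-on to Phase 1b is narrower than the protocol's sentence. The narrower wording fits the set's stated purpose and the Phase 1b-only assessment, but it should be recorded as a clarification.

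**Conclusion.** The concern holds. SAP 6.2.1 contradicts Protocol 9.7.1.2, the synopsis, the replacement rule in Protocol 9.5.1.3 and its own statement of purpose. Applied literally, it can lose at most one subject at Dose Level 1, which would turn a reported rate of 8.3% to 16.7% into 0%.

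This rests on three assumptions: one DLT occurred at that dose level, it prevented the second eribulin dose, and the set is programmed as the SAP words it. The first two cannot be checked from the documents. On the third, SAP section 9 places derivation rules in separate specifications that are not available here. The actual error may therefore be zero. The dose decision was based on a count of subjects with a DLT and has been made, and no efficacy result depends on this set. The correction should be made, but it does not threaten the trial's main efficacy conclusions.

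**What to change.** In SAP 6.2.1, change the add-on so that it covers subjects in Phase 1b who had a DLT, whether or not they completed cycle 1. Record the Phase 1b limit as a clarification of the protocol's unrestricted sentence.

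Align the rest of the definition with Protocol 9.7.1.2, or document the difference as Protocol 9.7.5 requires. In particular, the SAP omits the protocol's condition that cycle 1 completers have sufficient safety evaluation.

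Report later DLTs, and any DLT-type events in Phase 2, separately as counts or listings outside this set. Protocol 9.7.1.8.2 already asks for subsequent DLTs to be reported.

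The cost is a small edit to one SAP definition and a check that the programming specification matches it. No new data are needed.
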